6.4.5 Analysis of neutralization activity and correlation with serum concentrations

6.4.5.1 Primary analyses of neutralization magnitude-breadth curves

To address Primary objective 3, at each specified timepoint, the area-under-the-magnitude-breadth curve (AUC-MB) to a global panel of pseudoviruses (57) will be computed for each participant in the PP cohort with evaluable neutralization ID₅₀ or ID₈₀ data, as described in (58). Magnitude–Breadth (M-B) curves maybe employed to display individual- and group-level response breadth as a function of magnitude. Response breadth is defined as the percentage of viruses in the panel with neutralization titer above certain thresholds. Two choices are to compare the M-B curves among arms, as follows: a non-parametric Wilcoxon rank sum test on the subject-specific area-under-the M-B curve (AUC M-B) or a Kolmogorov-Smirnov type test on the 2 group-average M-B curves. Simulations can be used to obtain 2-sided p-values for the latter test. Second, a weighted-average score-like variable may be constructed to account for the correlations between virus isolates as an integrated magnitude of responses to multiple isolates. Similar group comparison methods described in the first approach may be adopted. Details of either approach will be described in the SAP.

6.4.5.2 Secondary analyses of correlations between serum concentrations and serum neutralization levels

To address Secondary objective 1, pharmacodynamics (PD) models based on either linear or non-linear mixed effects models will be performed to characterize the correlation between serum concentration (observed or popPK model-predicted) and serum neutralization against each virus or the AUC-MB of serum neutralization against the panel. Data from all enrolled participants will be analyzed regardless of how many administrations and how much mAb dose they received (MITT analysis). Similar to the popPK analysis, data from specimens collected outside of the visit window may be included in the PK/PD analyses that account for the actual specimen collection time, and the actual time and dose amount of each product administration. Since the exact date of HIV infection is unknown, any serum level data from blood draws 4 weeks prior to an infected participant's last seronegative sample and thereafter may be excluded. All data from HIV-infected participants who have no seronegative samples postenrollment may be excluded from the analysis.

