5.1 Primary objectives and endpoints

Primary objective 1:

To evaluate the safety and tolerability of PGDM1400LS when administered via intravenous (IV) or subcutaneous (SC) routes (Part A) and of PGDM1400LS, VRC07-523LS and PGT121.414.LS when administered in sequence IV or SC (Part B)

Primary endpoints 1:

- Local and systemic Solicited AEs, laboratory measures of safety, Unsolicited AEs, and SAEs
- Early discontinuation of administration and reason(s) for discontinuation and early study termination

Primary objective 2:

To evaluate the serum concentrations and pharmacokinetics of PGDM1400LS after a single administration (Part A) and of PGDM1400LS, VRC07-523LS, and PGT121.414.LS after each three-mAb administration (Part B)

Primary endpoint 2:

Serum concentrations of PGDM1400LS, VRC07-523LS and PGT121.414.LS at prespecified timepoints among participants who received all scheduled product administrations

Primary objective 3:

To evaluate the individual mAb-specific serum neutralizing activity after single product administration of PGDM1400LS (Part A) and after each three-mAb administration of PGDM1400LS, VRC07-523LS and PGT121.414.LS (Part B)

Primary endpoint 3:

Magnitude and breadth of neutralizing activity measured with Env pseudotyped viruses specific for either PGDM1400LS, VRC07-523LS or PGT121.414LS in TZM-bl cells at prespecified timepoints among participants who received all scheduled product administrations

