5.2 Secondary objectives and endpoints

Secondary objective 1:

To correlate serum concentrations of PGDM1400LS, VRC07-523LS and PGT121.414.LS with corresponding virus neutralization titers in serum

Secondary endpoints 1:

- Serum concentrations of PGDM1400LS, VRC07-523LS and PGT121.414.LS at prespecified timepoints for all participants in all groups regardless of how many product administrations and how much product they received
- Magnitude of serum neutralizing activity measured with mAb-specific Env-pseudotyped viruses in TZM-bl cells at prespecified timepoints for all participants in all groups regardless of how many product administrations and how much product they received

Secondary objective 2:

To determine whether the mAbs maintain their expected combined magnitude and breadth of serum neutralizing activity after each PGDM1400LS, VRC07-523LS and PGT121.414.LS three-mAb administration (Part B) as predicted by the known magnitude and breadth of neutralization of the corresponding mAb combinations as non-infused clinical products

Secondary endpoint 2:

Magnitude of neutralizing activity against a panel of Env-pseudotyped reference viruses that are sensitive to all three bnAbs in TZM-bl cells at selected timepoints for all participants in all groups regardless of how many product administrations and how much product they received

Secondary objective 3:

To determine whether anti-drug antibodies (ADA) are present

Secondary endpoint 3:

ADA titers in each group measured at prespecified timepoints for all participants in all groups regardless of how many product administrations and how much product they received

Secondary objective 4:

To evaluate the impact of body weight and other baseline covariates on the pharmacokinetics of PGDM1400LS, VRC07-523LS and PGT121.414.LS in both the weight-based and fixed-dose groups.

Secondary endpoint 4:

Serum concentrations of PGDM1400LS, VRC07-523LS and PGT121.414.LS at prespecified timepoints

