6.4.5.3 Secondary analyses of neutralization magnitude-breadth curves

To address Secondary objective 2, at each specified timepoint, the area-under-the-magnitude-breadth curve (AUC-MB) to a panel of Env-pseudotyped reference viruses that are sensitive to all three bnAbs will be computed for all participants with evaluable neutralization ID₅₀ or ID₈₀ data, as described in (58). Magnitude–Breadth (M-B) curves may be employed to display individual- and group-level response breadth as a function of magnitude.

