10.4 Neutralizing antibody assay

HIV-1-specific nAb assays will be performed on serum samples from study participants taken at post administration timepoint(s) and at baseline. The TZM-bl assay will test neutralization of mAb-specific viruses (one virus per mAb). The assay will also test the neutralization of a panel of viruses that exhibit a range of known sensitivities to PGDM1400LS, VRC07-523LS and PGT121.414.LS. The viruses will be selected from a global and/or clade-specific panel (57, 61) and may be modified by site-directed mutagenesis to be capable of measuring the activity of each mAb individually.

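### In Part B the stated primary neutralization analysis does not isolate each antibody as Primary objective 3 requires, and Secondary objective 2 has no predicted comparator

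*Protocol*

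**What the plan says.** Primary objective 3 (Protocol 5.1, repeated in SAP 3.1) opens: "To evaluate the individual mAb-specific serum neutralizing activity after single product administration of PGDM1400LS (Part A". For Part B it extends to all three antibodies after each triple administration. Its endpoint is: "Magnitude and breadth of neutralizing activity measured with Env pseudotyped viruses specific for either PGDM1400LS, VRC07-523LS or PGT121.414LS in TZM-bl cells".

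The analysis in Protocol 6.4.5.1 is different: "To address Primary objective 3, at each specified timepoint, the area-under-the-magnitude-breadth curve (AUC-MB) to a global panel of pseudoviruses (57) will be computed". The same section adds: "Response breadth is defined as the percentage of viruses in the panel with neutralization titer above certain thresholds". Section 6.1.3, which gives the precision for this objective, describes the target as a mean AUC-MB for each antibody, but does not say how an antibody-specific value is obtained.

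Section 10.4 plans two virus sets. On the first it says: "The TZM-bl assay will test neutralization of mAb-specific viruses (one virus per mAb". The second is a panel with a spread of sensitivities, taken from global and/or clade-specific sets. Its viruses may be mutated so that each antibody can be measured alone.

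Secondary objective 2 (Protocol 5.2) asks whether combined magnitude and breadth hold up "as predicted by the known magnitude and breadth of neutralization of the corresponding mAb combinations as non-infused clinical products". Its endpoint covers magnitude only. Section 6.4.5.3 computes AUC-MB to "a panel of Env-pseudotyped reference viruses that are sensitive to all three bnAbs will be computed for all participants" and then offers a display of the curves.

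Section 6.4.5.1 leaves details to the SAP. The SAP has no neutralization section. Its Overview leaves immunogenicity analysis to later revisions, and the outputs listed in its Section 9 are safety outputs.

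**The concern.** In Part A only PGDM1400LS is given, so a titre on any panel virus belongs to it. In Part B a titre on an unmodified virus reflects whichever of the three antibodies act on that virus. A global-panel AUC-MB then gives one combined value per participant and timepoint, and nothing in Section 6.4.5.1 divides it. Followed literally, the primary analysis in 80 of 95 participants answers a different question from its objective.

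Secondary objective 2 is an observed-versus-predicted question. An AUC-MB with no predicted value beside it describes the sera, but cannot show whether the infused antibodies kept their expected activity.

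**Working it through.** **1. The plan's own figure.** Section 6.1.3 and Table 6-4 use n = 12, a t-distribution and an SD of 0.5 or 1.0 on the log_e scale. The interval is exp(ln m ± t(0.975, 11) × SD/√12). With m = 50 and SD 0.5, the half-width is 2.201 × 0.5/3.464 = 0.318, which gives (36.4, 68.7) as stated. With SD 1.0 it gives (26.5, 94.4), also as stated. All 14 rows reproduce. The arithmetic is sound and depends only on n and SD. The question is which quantity it describes.

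**2. The descriptions side by side.**

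| | Objective | Endpoint | Assay section (10.4) | Analysis |
|---|---|---|---|---|
| Primary 3 | each antibody | antibody-specific viruses; magnitude and breadth | one specific virus per antibody; panel viruses may be mutated | AUC-MB, global panel, no per-antibody step |
| Secondary 2 | combined magnitude and breadth against prediction | magnitude; viruses sensitive to all three | panel with a spread of sensitivities | AUC-MB, viruses sensitive to all three; no predicted value |

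By contrast, Section 6.4.4.1 says explicitly that the concentration analysis is done for each antibody separately.

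**3. How much the antibodies overlap.** Figures 4-4 and 4-5 give first-week modelled coverage at ID80 >200. The 1-, 2- and 3-Active columns must be cumulative, because 94.1 + 73.4 + 26.7 = 194.2 exceeds 100. The share of covered viruses reached by two or more antibodies is (2-Active)/(1-Active).

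- Multi-clade, 4.2 g IV: 73.4/94.1 = 78.0%. Reached by exactly one: 94.1 − 73.4 = 20.7% of the panel.
- Multi-clade, 4.2 g SC: 59.5/86 = 69.2% at 35% bioavailability; 71.1/91.6 = 77.6% at 75%.
- Multi-clade, 60 mg/kg IV: 58.7/86.7 = 67.7% from the minima; 73.4/94.1 = 78.0% from the maxima.
- Other panels, 4.2 g IV: acute clade C 62.4/92.1 = 67.8%; CATNAP clade C 64.7/91.9 = 70.4%; CATNAP clade B 27.5/70 = 39.3%.

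**4. Breadth on one virus.** Under the breadth definition in Section 6.4.5.1, one virus per antibody gives each participant a breadth of 0% or 100% at any threshold. The area under that step is a function of the single titre, so the breadth half of Primary endpoint 3 adds nothing on this set.

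**5. The all-sensitive panel.** The protocol gives no cut-off for sensitivity. If it meant 3-Active at ID80 >200 (an assumption), the set would be 15.7% to 26.9% of the multi-clade panel at 60 mg/kg IV. From Table 4-6, at IC80 <50 mcg/mL, it is at most min(96, 74, 50) = 50% of the 208 viruses. Either way it omits viruses resistant to one or two antibodies, which are where a combination gains breadth.

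**6. Could a loss be hidden?** In Table 4-6 the VRC07-523LS column is taken as the one with 92% at IC50 <1 mcg/mL, as Section 4.7.4 states. At IC80 <50 mcg/mL VRC07-523LS alone reaches 96%, so losing both other antibodies costs at most 100 − 96 = 4 points. At IC80 <0.1 mcg/mL PGDM1400 reaches 44% and VRC07-523LS 23%, so the same loss costs at least 44 − 23 = 21 points. The effect depends strongly on the threshold.

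**The case against.** The strongest reply is that the pieces are already in the plan. Section 6.1.3 speaks of each antibody. Section 10.4 allows viruses from the same reference panel to be mutated so as to isolate one antibody. Titres on antibody-specific viruses are part of Secondary endpoint 1, Section 6.4.5.2 models neutralization virus by virus against concentration, and Section 6.4.7 provides descriptive summaries by arm and timepoint. The 15 Part A participants receive PGDM1400LS alone. The panel in Section 6.4.5.3 is the one that Secondary endpoint 2 names. The work is descriptive, and the SAP expects later revisions.

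All of that stands, and it rules out several stronger readings that a reader might infer:

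- That the trial cannot report individual-antibody activity in Part B. It can, because the specific viruses are assayed.
- That loss of PGDM1400LS activity would go unseen. Part A and the PGDM1400LS-specific virus would show it.
- That breadth on the all-sensitive panel is 100% by selection. Breadth is counted above titre thresholds, so it still varies with concentration and time.
- That a loss could move combined breadth by no more than 4 points. That holds only at the most lenient IC80 threshold, and AUC-MB integrates over thresholds.

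The reply does not remove the gap. Mutation is optional in Section 10.4, and Section 6.4.5.1 does not call on it. A secondary analysis of all enrolled participants is not the per-protocol primary analysis. Agreement between Section 6.4.5.3 and its endpoint does not supply the prediction that the objective names.

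**Conclusion.** The point holds for the stated analyses and does not extend to the data. Objectives, endpoints, assay section and analyses name different virus sets. In Part B (5 × 16 = 80 of 95 participants) the primary analysis, as written, gives a combined value where the objective asks for one per antibody. Secondary objective 2 lacks its comparator. The current SAP corrects neither.

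In the protocol's model, about two thirds to four fifths of covered multi-clade viruses are reached by two or more antibodies; on the clade B panel the share is 39%. These figures are indicative. They rest on the cumulative reading of the columns, on parental PGT121 and PGDM1400, and on panels other than the global one, for which the documents give no overlap. The attribution problem applies to unmodified viruses. It would not arise if the sponsor committed to mutated viruses that isolate each antibody.

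**What to change.** Make both changes in the protocol text and in the SAP revision, before neutralization data are analysed.

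1. **Primary objective 3, Part B (6.4.5.1).** For each antibody, analyse log ID50 and log ID80 on its specific virus, with geometric mean titre and 95% CI by arm and timepoint. Keep breadth in the endpoint only if several specific or mutated viruses per antibody are used. Report the unmodified global-panel AUC-MB as a separate, combined analysis. Align Section 6.1.3 and Table 6-4 with the quantity chosen. The tabulated intervals can stay if an SD of 0.5 to 1.0 is also assumed for these titres; the documents give no SD for them.

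2. **Secondary objective 2 (6.4.5.3).** Per participant, compute log(observed/predicted) for ID80 or AUC-MB, and report the mean ratio with 95% CI by arm. Predict from the three measured serum concentrations and the clinical-product IC80s, and name the rule that combines the antibodies (Bliss-Hill is one option; the documents name none). Keep the all-sensitive panel for magnitude, as the endpoint says. Use the panel with a spread of sensitivities, already planned in Section 10.4, for breadth.

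The cost is wording and modest extra analysis. Concentration and neutralization assays draw on the same stored serum (Appendix G), so no new participant samples are needed and the sample size is unchanged. The IC80s of the clinical products on the chosen viruses must be available; this is assumed, since the objective treats them as known.

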6.4.5.3 Secondary analyses of neutralization magnitude-breadth curves

To address Secondary objective 2, at each specified timepoint, the area-under-the-magnitude-breadth curve (AUC-MB) to a panel of Env-pseudotyped reference viruses that are sensitive to all three bnAbs will be computed for all participants with evaluable neutralization ID₅₀ or ID₈₀ data, as described in (58). Magnitude–Breadth (M-B) curves may be employed to display individual- and group-level response breadth as a function of magnitude.

6.4.6 Analysis of ADA and other non-neutralizing functional activities

For the analysis of ADA (Secondary objective 3), data from enrolled participants will be used regardless of how many administrations they received (MITT). For Exploratory objectives regarding mAb functionality, data from enrolled participants who received all scheduled administrations PP will be used. Assay results that are unreliable or from HIV-infected participants postinfection will be excluded. Additional exploratory analyses examining the impact of confirmed positive ADA on PK will be described in the SAP.

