5.3 Exploratory objectives

Exploratory objective 1:

To determine whether any confirmed positive ADA samples have functional activity that impacts the neutralizing activity of PGDM1400LS, VRC07-523LS and PGT121.414.LS

Exploratory objective 2:

To further evaluate non-neutralizing anti-viral activities, additional assays (eg, ADCC, ADCP, virion capture) may be performed for activities that the PGDM1400LS, VRC07-523LS and PGT121.414.LS are shown to exhibit in vitro

Exploratory objective 3:

To conduct analyses related to predicting serum neutralization over time against a set of potentially exposing viruses in a future efficacy trial for ranking and down-selecting bnAb regimens

Exploratory objective 4:

To conduct analyses related to furthering the understanding of HIV, passive immunity, immunology, vaccines, and clinical trial conduct.

6 Statistical considerations

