6.4 Statistical analyses

This section describes the final study analyses, unblinded as to treatment arm assignment. All safety data from enrolled participants will be analyzed according to the initial randomization assignment regardless of how many study product administrations and how much study product they received. In the rare instance that a participant receives the wrong treatment at a specific study product administration time, the Statistical Analysis Plan (SAP) will address how to analyze the participant's safety data. Analyses of safety data are modified intent-to-treat (MITT) in that individuals who are randomized but not enrolled do not contribute data and hence are excluded. Because of the brief length of time between randomization and enrollment—typically no more than 4 working days—very few such individuals are expected. The primary analysis of mAb concentration and anti-viral functional activity data are per-protocol (PP) in that only individuals who receive the expected mAb at the expected dose level within the expected visit window contribute data. Secondary analysis will also involve the MITT cohort, and when necessary account for the actual specimen collection time, and the actual time and dose amount of each product administration.

Analyses for primary endpoints will be performed using SAS and R. Additional software may be used to perform non-compartmental PK and population PK analyses (eg, Monolix). All other descriptive and inferential statistical analyses will be performed using SAS, StatXact, or R statistical software.

No formal multiple comparison adjustments will be employed for multiple primary or secondary endpoints. However, multiplicity adjustments will be made for certain primary or secondary endpoint assays, as discussed below, when the assay endpoint is viewed as a collection of hypotheses (eg, testing multiple pseudo-viruses to determine a positive antiviral functional activity response). Unless otherwise noted, all statistical tests will be 2-sided and will be considered statistically significant if $p < 0.05$.

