7.3.3 Discontinuing study product administration for a participant

Under certain circumstances, an individual participant's study product administrations will be permanently discontinued. Specific events that will result in stopping a participant's study product-administration schedule include:

- Co-enrollment in a study with an investigational research agent (rare exceptions allowing for the continuation of study product administrations may be granted with the unanimous consent of the HVTN 140/HPTN 101 PSRT)
- Clinically significant condition (ie, a condition that affects the immune system or for which continued study product administrations and/or blood draws may pose additional risk), including but not limited to the following:
 - HIV infection
 - Any grade 4 local or systemic Solicited or Unsolicited adverse event (AE) that is subsequently considered to be related to study product administration
 - Grade 3 clinical AE that is subsequently considered to be related to study product administration with the exception of fever, vomiting, and subjective local and systemic symptoms. For grade 3 infusion site erythema and/or induration, upon review, the HVTN 140/HPTN 101 PSRT may allow continuation of study product administration
 - Any grade 3 or 4 lab abnormality confirmed by a repeated value that is subsequently considered to be related to study product;
 - SAE that is subsequently considered to be related to study product administration
 - Clinically significant hypersensitivity or mAb reaction including, but not limited to, type 1 hypersensitivity reaction, urticaria, or serum sickness associated with study product administration. Consultation with the HVTN 140/HPTN 101 PSRT is required prior to subsequent study product administrations following any hypersensitivity reaction associated with study product administration
- Investigator determination in consultation with Protocol Team leadership (eg, for repeated nonadherence to study staff instructions)

Participants discontinuing study product for reasons other than HIV infection should be counseled on the importance of continuing with the study and strongly encouraged to participate in follow-up visits and protocol-related procedures per the protocol for the remainder of the trial, unless medically contraindicated (see HVTN 140/HPTN 101 SSP).

Participants diagnosed with HIV infection during the study should be encouraged to participate in follow-up visits as indicated in Section [9.12](#).

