10.6 ADA functional assay

A functional ADA assay will be used to characterize any positive activity that is observed in the ADA detection assays. Functional activity will measure a reduction in PGDM1400LS, VRC07-523LS and/or PGT121.414.LS neutralizing activity against a qualified virus in the TZM-bl assay.

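### On its natural reading, Protocol 6.4.6 gives the ADA-function analysis (Exploratory objective 1) a narrower set than ADA detection, leaving out ADA-positive Part B participants whose dosing stopped early

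*Protocol*

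**What the plan says.** Protocol Section 6.4.6 sets two populations in adjacent sentences. ADA, identified there as Secondary objective 3, is analysed in the MITT set. This agrees with Secondary endpoint 3 in Section 5.2: "ADA titers in each group measured at prespecified timepoints for all participants in all groups regardless of how many product administrations". The next sentence reads: "For Exploratory objectives regarding mAb functionality, data from enrolled participants who received all scheduled administrations PP will be used". Section 6.4 describes PP as the set in which "only individuals who receive the expected mAb at the expected dose level within the expected visit window contribute data".

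Exploratory objective 1 (Section 5.3) is "To determine whether any confirmed positive ADA samples have functional activity that impacts the neutralizing activity of PGDM1400LS, VRC07-523LS and PGT121.414.LS". Section 10.6 gives the laboratory scope: "A functional ADA assay will be used to characterize any positive activity that is observed in the ADA detection assays". Neither limits the samples to participants who completed dosing.

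Section 7.3.3 lists among the events that stop a participant's product schedule: "Clinically significant hypersensitivity or mAb reaction including, but not limited to, type 1 hypersensitivity reaction, urticaria, or serum sickness". It also asks sites to encourage such participants to remain in follow-up. In Part B, Appendix G schedules ADA samples at Days 0, 112 and 280.

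The SAP repeats the objectives and the general PP/MITT text (Sections 3 and 8) but has no section on ADA or ADA function. Its overview says later revisions are expected to cover immunogenicity data.

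**The concern.** Whether ADA is functional is a question asked of people who have ADA, so the relevant set is everyone with a confirmed positive sample. Completing both Part B administrations is a post-treatment condition. If a reaction linked to ADA is what stops dosing, restricting to completers selects on something related to the outcome.

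The practical risk lies in the report. A participant could appear as ADA-positive in the detection table, have a functional result on file, and be missing from the functional summary. If that person is the only functional positive, the summary would show none.

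**Working it through.** The documents give no sample size or precision figure for ADA or ADA function, so there is nothing to reproduce. The check compares analysis sets, followed by one illustration of scale.

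**1. Which sentence governs Exploratory objective 1?**
- The MITT sentence in 6.4.6 is tied to Secondary objective 3 only.
- The PP sentence covers exploratory objectives, in the plural, on mAb functionality. Exploratory objective 1 concerns ADA that impairs mAb neutralization, and the sentence sits in the ADA section.
- No other part of the protocol or SAP assigns it a set.

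The natural reading is therefore PP. If that reading is rejected, the objective has no stated analysis set.

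**2. Does PP match the stated scope?** No. Sections 5.3 and 10.6 cover any positive; PP covers only positives in participants with all scheduled administrations.

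**3. Who is in one set and not the other?**

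| Situation | ADA detection (MITT) | ADA function (PP reading) |
|---|---|---|
| Part A, single infusion completed | in | in |
| Part B, dosing stopped after the first administration | in | out |
| Part B, second administration started but not completed | in | out |
| Part B, reaction after a completed second administration | in | in |

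The table assumes that doses given were otherwise per protocol. In the second row, Day 112 and Day 280 samples can still exist if the participant stays in follow-up. The third row is possible because the three mAbs are given one after another (Section 8.4), so a reaction to one can leave the others ungiven.

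**4. Scale (illustration only).** Part B has 5 groups × 16 = 80 participants. Assume the infusion-reaction rates quoted in Section 4.9 for VRC01/placebo, 1.7% and 4.8% of participants.
- Expected number with a reaction: 80 × 0.017 = 1.4; 80 × 0.048 = 3.8.
- P(at least one) = 1 − (1 − p)^80: 0.75 and 0.98.
- At an assumed 0.5%: 80 × 0.005 = 0.4 expected; P(at least one) = 0.33.

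Under these rates, the counts are upper bounds on participants lost through reactions. Only a reaction that stops dosing before the second administration is complete removes someone from PP, and only those who are also ADA-positive matter here.

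**The case against.** The PP sentence does not name Exploratory objective 1. Section 6.4.1 lists mAb functionality and ADA as separate variables, and the plural could be met by Exploratory objectives 2 and 3. This stands as far as it goes: the PP reading is natural, not explicit. But the alternative leaves the objective without a set, and the same clarification is needed.

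Section 6.4 and SAP Section 8 add that secondary analysis will also use the MITT cohort. That text concerns mAb concentration and anti-viral functional activity. Even if it reaches ADA function, it makes MITT secondary to a set that does not match the objective.

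The functional results would be produced anyway under 10.6, and ADA assays may be run in reaction work-ups (10.7). That is true, so what is at stake is which results enter the summary, not whether they exist.

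A reader might infer that the participants whose ADA matters most are the ones removed. The documents do not show this. Someone who reacts after a completed second administration stays in PP. Section 4.9 reports that in the VRC01 efficacy trials 95% of related AEs fell within three days of infusion, so many first-dose reactions would come before the first post-dose ADA sample at Day 112. Section 7.3.3 also foresees consultation before any further dosing after a hypersensitivity reaction, so a reaction need not always end dosing.

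A reader might also take a loss of 12–20% from earlier VRC07-523LS trials: 440 of 500 planned IV/SC administrations given in HVTN 127/HPTN 087 (100 participants × 5), and 4 of 20 repeat doses missed in VRC 605 (41 of 45 given). These are doses, not participants; one person can miss several. They are missed for any cause, and HVTN 127/HPTN 087 ran five doses over 64 weeks against one repeat dose here. They do not convert into a share of ADA-positive participants lost.

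**Conclusion.** The mismatch is real but narrow. Section 6.4.6, read naturally, restricts Exploratory objective 1 to a set smaller than its own definition and smaller than the set used for ADA detection. The affected participants are those in Part B whose dosing stops before the second administration is complete and who have a confirmed positive ADA sample. Their exclusion may be related to ADA; the documents do not establish that it is.

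The number cannot be derived from the documents. A few of 80 at most is a judgement, resting on the assumption that VRC01/placebo reaction rates indicate the scale. Section 4.9 reports no ADA to date in trials of VRC01-class mAbs, PGT121 or PGDM1400, so positives may be rare; in that case each omitted one carries more weight. No primary or secondary objective is affected.

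One might infer that the analysis of ADA impact on PK has the same defect. It does not: 6.4.6 sets no PP limit there and leaves the detail to the SAP.

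**What to change.** In Protocol 6.4.6, and in the SAP when its immunogenicity section is written, state that:

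- Exploratory objective 1 uses all confirmed ADA-positive samples from enrolled participants (MITT, the same set as Secondary objective 3);
- a PP version may be shown as a sensitivity analysis;
- the PP restriction applies only to the non-neutralizing mAb activities of Exploratory objective 2.

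The cost is one sentence in each document. Section 10.6 already provides for functional testing of any positive, so no visits, samples or assays are added, and a SAP revision covering these data is already expected.
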